4 INTRODUCTION

4.1 Background and rationale

Gingival recession is defined as the apical shift of the gingival margin with respect to the cemento-enamel junction it is associated with attachment loss and with exposure of the root surface to the oral environment (Cortellini and Bissada, 2018). The etiology of gingival recessions remains unclear. Among predisposing factors tooth brushing has been suggested. A few systematic reviews support or refute the association between tooth brushing and gingival recession. In one systematic review, among the 18 examined studies, one concluded that the toothbrushes significantly reduced recessions on facial tooth surfaces over 18 months, two concluded that there appeared to be no relationship between tooth brushing frequency and gingival recession, while eight studies reported a positive association between tooth brushing frequency and recession. Several studies reported potential risk factors like duration of tooth brushing, brushing force, frequency of changing the tooth-brushing technique (Cortellini and Bissada, 2018).

Large cohort studies have demonstrated that high standards of oral hygiene are essential for oral health, prevention and treatment of periodontal diseases. The most common means of removing plaque at home is tooth brushing. Substantial plaque reduction can be achieved by manual brushing and/or a variety of power toothbrushes (ADA, 2019; Rosema et al., 2016) with the aim of improving plaque removal efficiency. A Cochrane systematic review on powered toothbrushes (Heanue et al., 2003), which has been updated (Heanue et al., 2003; Yaacob et al., 2014), claimed that only oscillating-rotating brushes are safe and have better clinically effects in terms of plaque removal and inflammation reduction. It is understood that tooth brushing requires the application of shear forces to remove plaque and can damage the superficial keratinized epithelial layer of the gingival tissue and create a background of gingival lesions (De Nutte et al., 2018). Superficial gingival abrasions can be expected to heal naturally, but it is unclear to what extent gingival abrasion caused by tooth brushing is associated with gingival recession. Due to the possible causal relationship between tooth brushing, gingival abrasion and gingival recession, an assessment of gingival tissue abrasion and recession in manual and power brush users is required to help establish whether there could be an association between these factors (Rosema et al., 2014). In addition, the use of high frequency sonic brushes has been considered safe and has produced satisfactory results in reducing gingival and plaque indices compared with conventional brushes used by patients with gingivitis and periodontitis (Costa et al., 2007). To our knowledge, no previous studies have provided information on the effects (abrasion) of tooth brushing on gum tissue.

The Philips Sonicare DiamondClean® power toothbrush is more effective than the ADA Reference manual toothbrush to reduce supra gingival plaque and gingival inflammation by routine manual toothbrush users (Delaurenti et al., 2017). Based on a sample of 154 randomized subjects the Philips Sonicare FlexCare® Platinum toothbrush with Premium plaque control brush head significantly reduces gingival inflammation, gingival bleeding, and plaque following two and six weeks of home use, when compared to manual tooth brushing alone (Jenkins et al., 2017). Recently, a randomized and examiner-blind study (Ccahuana-Vasquez et al., 2018) comparing the reduction of gingivitis and plaque over an 8-week period shows that oscillating-rotating electric rechargeable brush handle (Oral-B® PRO 1000, D16U) with a round brush head with angled bristles (Oral-B® CrossAction, EB50) performed better than a premium sonic brush (Philips Sonicare DiamondClean® Toothbrush with AdaptiveClean brush head). Opposite conclusions are produced by Starke et al. and by Mirza et al., comparing the benefits in terms of plaque and bleeding reduction with the Philips Sonicare DiamondClean® Smart powered toothbrush and the Oral-B Genius 8000 powered toothbrush following a 42-day home-use period (Mirza et al., 2019; Starke et al., 2017). The advantage of using high-frequency, high-amplitude sonic powered toothbrushes is to decrease plaque and gingivitis significantly more effectively than manual toothbrushes (de Jager et al., 2017) but not more than the oscillating-rotating power toothbrush according to a recent single-Centre study, randomized, examiner-blind, parallel group design (Lv et al., 2018). A meta-analysis based on six studies and a total of 462 subjects concludes that the benefits in terms of bleeding and plaque reduction, in dental surfaces hard to clean such as lingual and

Confidential

proximal mandibular surfaces, are higher when using a sonic powered toothbrush than when using a manual toothbrush (Grender et al., 2013).

Philips Sonicare brush heads work with sonic technology: High-speed vibrations in the toothbrush handle power up to 62,000 brush movements per minute that whip up the toothpaste into gentle cleaning bubbles, driving them deep between the teeth and the gum for additional cleaning. The sonic toothbrush Philips Sonicare ProtectiveClean has an intuitive pressure sensor that helps patients to guide their brushing technique. One of the advantages of using this toothbrush is that pressure sensor provides real-time feedback so patient will adopt a softer touch to protect teeth and gums. This toothbrush works on 2 modes to remove plaque gently and effectively. On some Philips Sonicare sonic brushes, a program named "Gum Care" also adds an extra minute of reduced-power brushing to gently massage the gums, improving gum health. In addition, the BrushSync feature tracks brush head effectiveness based on brushing time and pressure and alerts patients when it is time for replacement.

The toothbrush head Philips Sonicare Optimal Plaque Defense possesses densely-packed, high-quality bristles that remove up to 7x more plaque than a manual toothbrush (Philips Oral Healthcare, unpublished data). This brush head works with a sonic technology, high-speed vibrations in the toothbrush handle power up to 62,000 brush movements per minute that whip up the toothpaste into gentle cleaning bubbles, driving them deep between the teeth and the gum for cleaning. Philips Sonicare ProtectiveClean has an intuitive pressure sensor that helps patients to guide their brushing technique. This pressure sensor provides a real-time feedback, thus encouraging the subject to adopt a softer touch in order to protect his/her teeth and gums. This feature is one of the benefits of using this toothbrush. This toothbrush works on 2 modes to remove plaque gently and effectively. The Gum Care mode also adds an extra minute of reduced -power brushing to gently massage the gums, improving gum health

The Philips Sonicare Optimal Gum Care brush head was found to be superior to a manual toothbrush in reducing gingival inflammation and gingival bleeding. A recent clinical study compared the plaque removal efficacy of Philips Sonicare 2 Series versus a manual toothbrush. One-hundred and thirty-three (133) healthy adults (mean age 40.7 years, 103 females and 30 males) were included in a parallel, examiner-blinded clinical trial. Eligible subjects were non-smokers, aged 18-65 years who were routine manual toothbrush users. Enrolled participants had a minimum average plaque following 3-6 hours of plaque accumulation. All subjects were dispensed study products per randomization, either Philips Sonicare 2 Series power toothbrush or a manual toothbrush. Study subjects assigned to the Sonicare treatment group were instructed to brush at home twice daily for two minutes using the 'Clean' mode. Study subjects assigned with the manual toothbrush were instructed to brush twice daily per their regular technique. 3-6 hours plaque accumulation and plaque removal was assessed during a second visit 14 days after the initial visit. Safety was assessed per subject report and intraoral examination. The results of this study showed that Philips Sonicare 2 Series was statistically superior to manual toothbrush in reducing plaque including posterior interproximal areas (Milleman et al., 2014, unpublished data). However, electric toothbrush heads become less effective after 3 months of use.

Usually patients brush their teeth with a toothpaste. To minimize the bias of using abrasive toothpaste the choice of a sodium monofluorophosphate (1450 ppm F) toothpaste (elmex® SENSITIVE PROFESSIONAL) with a low degree of abrasion as defined by the relative dentine abrasion (RDA) was made. RDA –is an index of tooth abrasion by toothpaste. The RDA scale ranges from 0 to 250. The 0-70 range is considered as low abrasion, i.e. safe for cement, dentine and enamel (González-Cabezas et al., 2013). According to this standard, toothpastes with an RDA value below 250 can be used safely for a lifetime. However, the RDA value is only one of the factors that cause tooth wear during brushing. An *in vitro* study concludes that, regardless of the properties of the toothpastes (desensitizing and/or anti-erosive) the lower surface abrasion is associated with higher concentration of Ca^{2+} and PO_4^{3-} , presence of Sn^{2+} , higher percentage weight of solid particles, smaller particle size, and lower wettability (João-Souza et al., 2017).

Therefore, the aim of this study is to compare the gingival abrasion of a sonic toothbrush (Sonicare ProtectiveClean® Optimal Plaque Defense head) as test group with a conventional manual toothbrush (control group) in regular patients attending the Service of Odontology of the Hôpital Rothschild (AP-HP).

4.2 Investigational Product indications and contra-indications

Indications

Electric toothbrushes are intended for all patients today and specially for (Sussalan et al., 2018):

- Orthodontic patients;
- Those who are on supportive periodontal therapy;
- Patients with prosthodontic or dental implants;
- For hospitalized patients;
- Individuals with low manual dexterity, such as children and the handicapped.

Contraindications

- Thin gingival phenotype
- Patients with cardiac pacemakers -As they can result in electrical interference with the normal functioning of implantable cardiac devices.

4.3 Risk-Benefit Assessment

The investigational and control devices used in this study are standard devices that are normally used for routine oral hygiene. Very few adverse effects are expected. On the other hand, 50% of the patients may benefit from using the investigational product as it is expected to perform better than a conventional toothbrush in terms of plaque removal and gingival abrasion. The clinical procedures performed are standard procedures.

5 STUDY OBJECTIVES

5.1 Primary Objective and Endpoint

5.1.1 Primary objective

Primary endpoint variables will be used to assess and to compare the gingival abrasion of a sonic toothbrush (Sonicare ProtectiveClean® Optimal Plaque Defense head) in a test group with a conventional manual toothbrush (control group) in regular patients attending the Service of Odontology of the Hôpital Rothschild (AP-HP). These variables will be recorded at the mandible and at the maxillary on the buccal aspects of teeth 6, 4, 3, 1 in each quadrant. If one these teeth is missing, the adjacent mesial tooth will be evaluated. If ever the adjacent mesial tooth is missing the distal tooth is chosen.

5.1.2 Primary endpoint

Evaluation of the gingival abrasion (GA): Macro-relief scoring.

A first method for the evaluation of gingival abrasion (GA) will consist in a method of macro-relief scoring of gingival tissue as described previously by Perin *et al.* with skin tissue. This evaluation consists of acquiring macroscopic views of each investigated surface and then classifying them by observers according to a reference groups of defined abrasion intensity. This evaluation scoring,

using photo grading technique, allow delayed and blinded scoring, independent of whole-subject appearance, thus decreasing subjectivity (Perin et al., 2000).

The macro-relief gingival abrasion scoring technique consists of acquiring macroscopic photographs of each gingival quadrant at each time point. Observers will score these photographs in a double-blind manner by comparing the different photographs with a photonumerical reference scale used as standard. This scale, composed of 5 criteria each scored from 0 to 3, has already been retained by observers as being representative of the different grades of gingival abrasion. The final score will range from 0 (no abrasion) to 15 (severe gingival abrasion).

5.2 Secondary Objectives and Endpoints

5.2.1 Secondary objectives

The secondary objectives aim at assessing the effects of a sonic toothbrush versus a conventional manual toothbrush in terms of plaque elimination, gingival inflammation reduction minimizing gingival recession on the gingival tissue of patients in routine dental treatments.

Another secondary objective aims to compare gingival abrasion evaluation techniques.

5.2.2 Secondary endpoints

The investigator will perform the assessment of evolution of secondary objectives after 90 days, using the following endpoints:

- ✓ Comparison of gingival color;
- ✓ Presence of plaque -Plaque index, PI - (Silness and Löe, 1964)
- ✓ Presence of inflammation BOP (Ainamo and Bay, 1975)
- ✓ Presence and/or amount of gingival recession (REC).

5.2.2.1 *Changes in gingival color*

The evaluation of gingival coloring will be conducted by trained examiners and will consist in extracting each individual visual component of the gingival surface color, based on sensory analysis. This method has already been applied to describe the intensity of skin coloring (red /green/blue component) as well as luminosity, the brightness and transparency (Musnier et al., 2004) and will be applied to each subject's gingival tissue.

Photographed views will be taken according to the standard shooting protocol used in the hospital department, which ensures that all photographs are made in the axis to facilitate proper recording with minimal distortion. A control of image reproducibility will be done by an examiner with image analysis software. A previous study (Kerner et al., 2007) has shown that this method is highly correlated with clinical measurements. During photo shooting, an internal colored reference chart will be photographed in the vicinity of the photographed gingival tissue, as extensively explained by Van Poucke et al in 2010 (Van Poucke et al., 2010).

Regarding the periodontal parameters, a full-mouth examination will be performed.

5.2.2.2 *Probing pocket depth (PD)*

PD will be measured before the test/control treatment by one and the same examiner by using the PCP-UNC 15 (Hu-Friedy® Chicago, IL, USA) probe throughout the study. The probing depth will be assessed at the buccal aspects of teeth 16,14,13,11. All measurements will be adjusted to the nearest 1.0 mm.

5.2.2.3 *Gingival margin recession (REC)*

Gingival margin recession will be measured from the cemento-enamel junction to the marginal position of the gingiva with PCP-UNC 15 (Hu-Friedy® Chicago, IL, USA) probe. The measurements will be assessed at the middle of the buccal gingival recession.

5.2.2.4 *Bleeding on marginal probing (BOP)*

Gingival inflammation (GI) will be assessed as bleeding on marginal probing (BOP) using the index as described by Ainamo & Bay (Ainamo and Bay, 1975). GI uses a 0 to 3 scale to measure the presence of inflammation or not on six sites (mesio-buccal, buccal, disto-buccal, mesio-lingual, lingual, and disto-lingual) on all teeth, according to the following criteria: 0: absence of inflammation; 1: visible inflammation and no bleeding; 2: visible inflammation and bleeding on probing; 3: obvious inflammation and spontaneous bleeding.

BOP is considered as dichotomous variable. BOP uses 0 and 1 scale. 0: no bleeding on probing; 1: bleeding on probing including 4 sites per tooth. The percentage of bleeding will be calculated as following: number of sites with bleeding / number of sites assessed X 100.

5.2.2.5 *Plaque index (PI)*

Plaque index (PI) described by Silness & Löe (Silness and Löe, 1964) uses 0 to 4 classes to assess the presence of plaque or not on six sites (mesio-buccal, buccal, disto-buccal, mesio-lingual, lingual, and disto-lingual) on all teeth, according to the following criteria: 0: absence of plaque; 1: non visible plaque but detectable with a probe; 2: visible plaque not detectable in the interproximal areas; 3: visible plaque in interdental spaces also.

6 STUDY DESIGN

6.1 Type of study

This will be a monocentric, interventional, reference-controlled, randomized, single blind, and superiority study.

The examiner will be blind regarding the investigational products.

6.2 Study Design

[figure not shown]

Figure 2: Study diagram

6.3 Treatment groups

The choice of the tooth brushing instrumentation and the brush group will be done randomly by one operator. In addition, these groups will be selected for brushing with or without instructions of the operator with manual or electric toothbrush. The Examiner will be blind and, at any stage of the measurements not informed of the distribution / repartition of the brush group / selected devices.

- ✓ Brush group 1: Sonicare ProtectiveClean® toothbrush (HX6848/92 Philips) equipped with a C2 Optimal Plaque Defense head (HX9022/10 Philips) + oral hygiene instructions + Manufacturer's instructions + sodium monofluorophosphate (1450 ppm F) toothpaste (elmex® SENSITIVE PROFESSIONAL Colgate-Palmolive) with a low degree of abrasivity.
- ✓ Brush group 2: Inava® 20/100 (Code ACL: 3401561130767) manual toothbrush + oral hygiene instructions + Manufacturer's instructions + sodium monofluorophosphate (1450 ppm F) toothpaste (elmex® SENSITIVE PROFESSIONAL Colgate-Palmolive) with a low degree of abrasivity (= 79).

1st Group: Electric toothbrush + manufacturer's instructions + professional recommendations + sodium monofluorophosphate (1450 ppm F) toothpaste (elmex® SENSITIVE PROFESSIONAL)
2th Group: Manual toothbrush + manufacturer's instructions + professional recommendations + sodium monofluorophosphate (1450 ppm F) toothpaste (elmex® SENSITIVE PROFESSIONAL)

6.4 Randomization

Patients will be enrolled sequentially. Patients will be randomized to use either Philips Sonicare ProtectiveClean® or Pierre Fabre Inava® 20/100 toothbrushes (1:1) at inclusion in accordance with a central randomization table generated using a validated computer program. Randomization will be stratified by study site and performed using, a permuted block of 4. Each randomization number will be assigned when a screened patient will be deemed eligible. Toothbrush allocation only depends on the time sequence in which patients enter the study, thus minimizing the selection bias. Treatments will be allocated in accordance with the randomization number assigned to the patient.

6.5 Blinding /Unblinding

At first the eligible patients are randomized. After this step, the data for each patient of two groups (test and control) are collected. The examiner, laboratory and statistical procedures will be blind to the treatment.

6.6 Time and repartition of tooth brushing procedures

The randomization of the toothbrush and the brush group will be performed as previously described by the operator (see section 6.4). Subjects will receive a Sonicare ProtectiveClean® toothbrush (HX6848/92 Philips) equipped with a C2 Optimal Plaque Defense head (HX9022/10 Philips) or a standard manual toothbrush (Pierre Fabre Inava® 20/100) and a sodium monofluorophosphate (1450 ppm F) toothpaste (elmex® SENSITIVE PROFESSIONAL). The brushing duration will be inconspicuously measured in seconds with a stopwatch, while the participants are brushing. The mean duration of brushing will be 30 seconds per quadrant for manual or power brushers. All participants with their assigned toothbrush (being either the Philips Sonicare ProtectiveClean® 6809/04 or Inava® 20/100) will brush with manufacturers / professional recommendations. They will use a sodium monofluorophosphate (1450 ppm F) toothpaste. At the beginning of the study three and/or four 75 ml tubes of toothpaste will be given to each patient. It has been calculated that the dose of toothpaste per brushing was 1.21 g on average i.e. 217.8 grams for 90 days (Precisa®100C-3000D). The tubes of toothpaste are weighed at the beginning (average 108 g) and at the end of this study. It is thus possible to measure the global quantity of toothpaste used and the possible effect of this use on the surface texture of the gum tissue.

Thus, brushing time for the whole mouth will be 2 minutes for each patient from both toothbrush groups. The evaluation time and the consequences of brushing will be assessed immediately and 90 days later.

7 SELECTION AND WITHDRAWAL OF PATIENTS

7.1 Informed Consent

An informed consent form, written in accordance with the Declaration of Helsinki (see Appendix 1) and applicable laws of the country of interest will be obtained from all patients.

The patient will sign the informed consent form before being enrolled into the study, i.e. before screening assessments or any other study-related activity. The Investigator will explain the nature, purpose and risks of the study and provide the patient with a copy of the patient information sheet. The patient will be given sufficient time to consider the study implications before deciding whether to participate. Should there be any amendments to the final protocol such that this would directly affect the patient participation in the study, e.g. a change in any procedure, the informed consent

form will be amended to incorporate this modification and an informed re-consent will be obtained from the patient.

7.2 Eligibility Criteria

The volunteers will be informed on the background of the study and a written explanation will be given concerning the objectives and the involvement methods. They all will request to give their written consent prior the enrolment into the study.

Each patient entering the study must comply with all of the primary inclusion criteria and will be excluded if one or more exclusion criteria is met.

7.2.1 *Inclusion Criteria*

1. Dentate males and females must be at least 18 years and not more than 75 years of age
2. Patient able to understand and sign the informed consent prior to starting the study
3. Patient with a minimum of 3 teeth in each of the 4 quadrants and no/or pockets >4 mm
4. Ability and willingness to comply with all study requirements.

7.2.2 *Non-inclusion Criteria*

1. Pregnancy
2. Patient with cervical restorations
3. Current smoker
4. Patient with orthodontic banding
5. Patient with oral lesions or periodontal diseases
6. Patient who has been deprived of his/her freedom by administrative or legal decision or who is under trusteeship/guardianship
7. Patient already using an electric toothbrush
8. Patient with conditions or circumstances, which may prevent completion of study participation or interfere with analysis of study results, such as history of non-compliance, or unreliability;
9. Patient with non-plaque induced gingival diseases or localized gingival ulceration
10. Thin gingival phenotype
11. Patients with cardiac pacemakers to prevent any interference between the power toothbrush and the implantable cardiac device.

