8.1 Name and Description of the Investigational Product

In this study both products, Philips Sonicare ProtectiveClean® and the manual toothbrush (Pierre Fabre Inava® 20/100) will be used within the indications. The test sites will be treated with the investigational device following the instructions of this protocol.

Investigational devices will be made available to the investigation site by the Sponsor. If any defect in the Investigational Product is observed, the study manager or monitor will be informed. A sodium monofluorophosphate (1450 ppm F) toothpaste (elmex® SENSITIVE PROFESSIONAL) will be provided to the patient.

8.1.1 *Indications for use*

The indication studied is using of an electric toothbrush Philips Sonicare ProtectiveClean® HX6848/92 associated with a C2 Optimal Plaque Defense head HX9022/10, in routine oral hygiene and to assess the possible effects on hard and soft tissue.

8.1.2 *Duration of treatment*

The overall duration of the study for the patient will be 90 days from the time of the baseline.

8.1.3 *Packaging and Labelling*

The boxes will be labelled in accordance with ISO 14155:2011 (Paragraph 5.10). Labels will indicate that the device is exclusively intended for use in the study and will identify the study number, Sponsor and patient code.

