15.7 Investigator's Brochure

The Investigator Brochure is replaced by the Instructions For Use.

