19.2 Appendix 2: Philips Sonicare ProtectiveClean® Instructions for use

Philips Sonicare ProtectiveClean® - ©2014 Koninklijke Philips Electronics NV (KPENV).

The Sonicare toothbrush complies with the safety standards for electromagnetic devices. If you have a pacemaker or other implanted device, contact your physician or the device manufacturer of the implanted device before you use the Sonicare.

Package Insert

General Description

IMPORTANT

Read this user manual carefully before you use the appliance and save it for future reference.

DANGER

-Keep the charging base away from water.

Do not place or store it over or near water contained in a bathtub, washbasin, sink etc. Do not immerse the charger in water or any other liquid. After cleaning, make sure the charger is completely dry before you connect it to the mains.

WARNING

-The mains cord cannot be replaced. If the mains cord is damaged, discard the charger.

- Always have the charger replaced with one of the original type in order to avoid a hazard.
- Do not use the charger outdoors or near heated surface.
- Check if the voltage indicated on the appliance corresponds to the local mains voltage before you connect the appliance.
- If the appliance is damaged in any way (brush head, toothbrush handle or charger), stop using it. This appliance contains no serviceable parts. If the appliance is damaged, contact the Consumer Care Centre in your country (see chapter 'Warranty and support').
- This appliance can be used by children and by persons with reduced physical, sensory or mental capabilities or lack of experience and knowledge if they have been given supervision or instruction concerning use of the appliance in a safe way and understand the hazards involved. Cleaning and user maintenance shall not be made by children without supervision.
- Children shall not play with the appliance.

CAUTION

- Do not clean the brush head, handle or the charger in the dishwasher.
- If you have had oral or gum surgery in the previous 2 months, consult your dentist before you use the toothbrush.
- Consult your dentist if excessive bleeding occurs after using this toothbrush or if bleeding continues to occur after 1 week of use. Also consult your dentist if you experience discomfort or pain when you use the Philips Sonicare.

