- The Sonicare toothbrush complies with the safety standards for electromagnetic devices. If you have a pacemaker or other implanted device, contact your physician or the device manufacturer of the implanted device before to use.
- If you have medical concerns, consult your doctor before you use the Sonicare.
- This appliance has only been designed for cleaning teeth, gums and tongue. Do not use it for any other purpose. Stop using the appliance and contact your doctor if you experience any discomfort or pain.
- The Sonicare toothbrush is a personal care device and is not intended for use on multiple patients in a dental practice or institution.
- Stop using a brush head with crushed or bent bristles. Replace the brush head every 3 months or sooner if signs of wear appear. Do not use other brush heads than the ones recommended by the manufacturer.
- If your toothpaste contains peroxide, baking soda or bicarbonate (common in whitening toothpastes), thoroughly clean the brush head with soap and water after each use. This prevents possible cracking of the plastic.

Electromagnetic fields (EMF)

This Philips appliance complies with all applicable standards and regulations regarding exposure to electromagnetic fields.

Radio Equipment Directive

- Radio Equipment in this product operates at 13.56 MHz
- Maximum RF power transmitted by the Radio Equipment is 30.16dBm

Introduction

Congratulations on your purchase and welcome to Philips! To fully benefit from the support that Philips offers, register your product at www.philips.com/welcome.

Brush heads

Your Philips Sonicare comes with one or more brush heads which are designed to deliver superior results for your oral care needs.

Philips Sonicare BrushSync Technology

Your smart brush heads use a microchip to sync with your handle, enabling brush head replacement reminder. For more information regarding the brush head replacement reminder, see 'Features'. This symbol indicates the brush head is equipped with BrushSync technology. (Fig. 2)

Brushing modes

Your power toothbrush is equipped with clean mode.

Clean mode

Clean is a 2-minute mode. It gives you a thorough and complete clean and is recommended to be used with the C2 Optimal Plaque Control brush head.

Intensities

Your power toothbrush gives you the option to choose between low and high intensity.

Note: When you use the toothbrush for the first time, the default setting is the low intensity.

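### Non-inclusion criterion 11 names only cardiac pacemakers, narrower than the protocol's own reason and its appended manual, and no check before randomisation covers other implanted electronic devices

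*Protocol*

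**What the plan says.** Criterion 11 in Protocol 7.2.2, repeated word for word in the synopsis, excludes "Patients with cardiac pacemakers to prevent any interference between the power toothbrush and the implantable cardiac device". Section 7.2 makes the list operative: a patient "will be excluded if one or more exclusion criteria is met".

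Section 4.2 gives two contraindications to the electric brush, thin gingival phenotype and cardiac pacemakers. Its reason for the second is "As they can result in electrical interference with the normal functioning of implantable cardiac devices". Among the indications, the same section lists "Patients with prosthodontic or dental implants".

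The product manual in Appendix 2 (section 19.2) opens with a precaution: "If you have a pacemaker or other implanted device, contact your physician". Under its caution heading it repeats: "If you have a pacemaker or other implanted device, contact your physician or the device manufacturer of the implanted device before to use". Both times it also states that the brush meets electromagnetic safety standards. Section 15.7 fixes the manual's standing: "The Investigator Brochure is replaced by the Instructions For Use".

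Three sections bring the manual into the regimen. Section 6.3 lists the manufacturer's instructions among what each brush group receives, 6.6 has participants brush according to manufacturer and professional recommendations, and 8.3 refers to the appended notices for instructions for use.

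**The concern.** The protocol describes the same precaution with three different scopes, and the criterion that decides eligibility has the narrowest. Read literally, a patient with an implanted cardiac device other than a pacemaker (a defibrillator, to give an example that is not in the protocol) is eligible, although the reason in 4.2 applies to that patient. A patient with a non-cardiac electronic implant (a neurostimulator, again my example) falls outside both the criterion and its reason, but within the manual's precaution.

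At stake is one participant-safety step. The manual's advice applies before first use. In this trial first use comes at the same visit as consent and randomisation, and twice-daily home use for 12 weeks follows. If the question is not asked at the eligibility check, nothing later in the protocol obliges the investigator to ask it before the brush is used.

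**Working it through.** There is no stated figure to reproduce, so this is a comparison of texts and a check of timing.

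**1. Scope of each statement**

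| Place | Devices named | Action |
|---|---|---|
| 7.2.2 and synopsis, criterion 11 | Cardiac pacemakers | Exclusion |
| 4.2, contraindication | Cardiac pacemakers | Contraindicated |
| 4.2, reason given | Implantable cardiac devices | Explains the line above |
| Appendix 2, both warnings | Pacemaker or other implanted device | Consult before use |

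The reason in 4.2 is wider than the criterion, and the manual is wider than both. For pacemakers the protocol is stricter than the manual, since it excludes where the manual advises consultation. For every other implanted device it adds no step of its own.

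**2. Does another criterion cover the gap?** Of the 11 non-inclusion criteria, 1 concerns an implanted electronic device. The nearest general one, criterion 8, is about conditions that could prevent completion or disturb the analysis of results. It does not address interference between devices.

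**3. Does a study procedure cover it?**
- 9.3 lists for Day 1, in order: explanation, inclusion and non-inclusion criteria, consent, randomisation, product supply, the baseline measurements and photographs, and then the brushing session. No implant question or clearance is listed.
- 7.1 requires the risks to be explained but does not call for an implant question.
- 8.1 says the products "will be used within the indications". For other implants this adds nothing, because the contraindication in 4.2 is itself limited to pacemakers.
- 6.3, 6.6 and 8.3 deliver the manufacturer's instructions with the assigned brush, hence after allocation. The oral instructions set out in 8.3 concern brushing technique.

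The advice therefore reaches the sonic-arm patient, but as something to read and act on personally. It does not reach the eligibility decision.

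**4. What can the manual's phrase sensibly mean?** Taken literally, *other implanted device* would include dental implants, which 4.2 lists as an indication. The phrase cannot be copied into the criterion unqualified. Limiting it to active (electronic) implants is my interpretation.

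**5. Size.** The planned total is 60 in two equal arms, so the sonic arm is 60 / 2 = 30. The documents give no implant prevalence, and I assume none. The number of patients affected lies between 0 and 30. The upper limit is simply the arm size, not an expectation.

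**The case against.** The best defence is that the manual is part of the regimen. Sonic-arm patients receive it (6.3), are to brush according to it (6.6), and are supplied with the product several listed steps before the brushing session (9.3). A sponsor may exclude one named group outright and leave the rest to product labelling. The manual itself asks for consultation before use, not before randomisation. It does not contraindicate use, and it says the brush complies with electromagnetic safety standards. Criterion 11 also states its purpose in terms of the implantable cardiac device, so an investigator reading it by purpose could exclude a defibrillator. The words active implant, defibrillator and neurostimulator appear nowhere in the protocol. The consent pages are not in the text at hand and might mention implants.

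Much of this stands, and it limits the point. A reader might infer that a patient with another implant would start sonic brushing with no prompt to consult. The documents do not support that, because the manufacturer's instructions carry the prompt. Nor do they show that the sonic brush is hazardous for such patients, or that the manual forbids its use.

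The defence does not supply a check by the investigator. Reading the criterion by its purpose is possible but not required by its wording, and it does not help for non-cardiac implants. User advice handed over after allocation, at the visit where first brushing takes place, leaves little room to contact a physician or manufacturer. A warning in the patient information sheet would help but would not alter the eligibility criteria.

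**Conclusion.** The point holds as a minor participant-safety improvement. Criterion 11 and the contraindication in 4.2 are narrower than the reason in 4.2 and than the manual that serves as the trial's product reference. No eligibility criterion or investigator check applies the manual's precaution before randomisation and first use.

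The case is clearest for cardiac devices other than pacemakers, where the protocol's own reason applies and only its wording falls short. It is weaker for non-cardiac implants, where it rests on the manual alone and on reading *other implanted device* as an active implant. Between 0 and 30 patients could be affected, quite possibly none. The comparison between brushes, the endpoints, the sample size and the analysis are untouched.

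**What to change.** 1. Reword criterion 11 (7.2.2 and synopsis) and the contraindication in 4.2 to: *cardiac pacemaker or other implanted cardiac electronic device*.
2. For any other active (electronic) implant, dental implants not included, add a question at the existing inclusion/non-inclusion check. Document physician or device-manufacturer advice before first use of the sonic brush, preferably before randomisation, so that a negative answer becomes a screening failure and not a withdrawal from one arm.

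The cost is wording in 3 places (7.2.2, synopsis, 4.2) and one question, with its documentation rule, at a step that already exists. The downside is an occasional screening failure, or a delayed inclusion while advice is sought. Patients with dental implants are unaffected.
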